1.2 Trial Schema

1.3 Schedule of Activities

- Step 1: Enrollment and Intervention
 - Screening (including baseline assessment)

- Randomization by recruitment to test or control groups
- Informed Consent
- Access to control and test programs
- Regular Assessments up to 18 months
- Step 2: Data Analysis
 - Interim Data analysis will be 3 months, 6 months, 12 months and 18 months data.
- Step 3: Publication
 - Publication on protocol analysis and outcomes data is expected at 12 months and the end of 18 months

Section 2: INTRODUCTION

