 - Motivation to work: Assessed through self-reported scales or questionnaires.
 - Performance review scores: Obtained from employer records or self-reported performance evaluations.
- Estimand(s): The difference in mean scores of motivation and performance reviews between the intervention and control groups over the trial period.

Exploratory Objective(s):

Impact on rates of cancer progression, and recurrence

Clinical Question: What is the effect of Complement Theory's program on progression and recurrence of prostate, lung and colorectal cancers?

- Endpoint(s):
 - Cancer progression: Measured by changes in tumor size and changes in levels of biomarkers.
 - Recurrence: Incidence of cancer recurrence.
- Estimand(s): Directional trends evaluating the difference in proportions or rates of cancer progression and recurrence between the intervention and control groups during and post-trial follow-up.

Rationale for Excluding Breast Cancer from Exploratory Objective:

- Breast cancer, in particular, exhibits a longer average timeframe for recurrence when compared to prostate, lung and colorectal cancers. This longer latency could extend beyond the scope of our study's follow-up period, making it

challenging to accurately measure the program's impact on recurrence rates within the study's duration.

- By focusing on prostate, lung and colorectal cancers, we aim to assess the program's impact on cancers with more predictable progression patterns and well-established biomarkers, enabling a clearer evaluation of the Complement Theory's potential benefits in these specific cancer populations.

Impact on Total Healthcare Expenditure

Clinical Question: Does participation in Complement Theory's 12-month Live coactive Coaching program, focusing on Exercise and Meditation and supplemented with evidence-based information on Diet, Sleep, and other lifestyle practices, adjunct to the core treatment, lead to a reduction in total healthcare expenditure for cancer survivors?

- Endpoint(s): Total healthcare expenditure, including hospitalization costs, medication expenses, outpatient visits, and any other related healthcare services that we planned and unplanned, cancer and non-cancer, over the trial period.
- Estimand(s): The difference in mean total healthcare expenditure between the intervention and control groups over a specified period (e.g., at 12 months and 18 months from baseline).

3.1 Summary of objectives, endpoints and estimands:

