5.3 Inclusion Criteria

- Cancer Type : Breast, Prostate, Colorectal, Lung and Other Cancers
 - Other Cancers here refers all other cancer types apart from Breast, Prostate, Colorectal and Lung Cancer
- Cancer Stage: Stage 1 to 4
- Treatment Status: Has undergone any cancer-related treatment in last 12 months
- Age : 21 yrs and above
- Permission to access to last 1 year digital health records
- Access to smartphone or a tablet

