5.4 Exclusion Criteria

- Excludes individuals who have undergone surgery within the last 4 weeks or will undergo surgery in the next 4 weeks
- Participants declared medically unfit by their physicians to do physical exercise
- ECOG Score 3, 4 or 5

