8.4 Adverse Events and Serious Adverse Events

A serious adverse event (SAE) in this trial is defined according to the following severity grades:

- Grade 1: Mild discomfort, not interrupting normal activities
- Grade 2: Moderate discomfort, interrupts normal activities but not incapacitating
- Grade 3: Severe, resulting in disability or necessitating medical consultation (SAE)
- Grade 4: Requires hospitalization (SAE)
- Grade 5: Results in death (SAE)

Only events classified as Grade 3, 4, or 5 are considered SAEs within the context of this trial

- Time Period and Frequency for Collecting SAE Information
 - Time period
 - Start: Apr 15, 2024
 - End: Oct 15, 2025
 - Frequency
 - SAEs will be documented as they are reported by participants.
- Recording of SAEs
 - While prior studies suggest minimal evidence of SAEs resulting from exercise, diet, or meditation in cancer survivors, all SAEs encountered during this trial will be meticulously recorded. Participants can report SAEs directly via the app, or coaches may report on their behalf. Reports should include the severity grade, description of the event, and the participant's perspective on whether the SAE was related to trial interventions.
- Follow up of SAEs

- All participants will continue receiving standard care from their healthcare providers. In the event of an SAE, a dedicated physician will be assigned to assess the situation, provide immediate recommendations, and categorize the cause of the SAE based on discussions with the participant. This classification will also be documented.
- Regulatory Reporting Requirements for SAEs
 - SAEs must be reported to the Institutional Review Board (IRB) within 24 hours of the event's identification. Additionally, the Sponsor will ensure prompt notification of all investigators regarding any SAEs, enabling them to inform participants about potential risks and take any necessary precautions.
- The grading of adverse events is aligned with the Common Toxicity Criteria for Adverse Events (CTCAE) standards, which detail adverse events on a scale from 1 to 5. The complete CTCAE documentation is available on the National Cancer Institute's website: [NCI CTCAE Information](#).

Section 9: STATISTICAL CONSIDERATIONS

The analysis will be conducted on all participant data at the end of 3 months, 6 months, 12 months and 18 months (ie. end of the trial).

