9.1 Analysis Sets

- The analysis will include the following datasets:
 - Intent-to-Treat (ITT) set: Including all randomized survivors, regardless of their adherence with the entry criteria. This set will be used for the primary analysis of Quality of Life changes and cancer progression.
 - Per-Protocol (PP) set: Including participants who completed the trial according to the protocol without significant deviations. PP set is a subset of ITT set, excluding survivors with major protocol deviations or those who do not complete the trial. This set will be used to summarize efficacy and support sensitivity analyses.

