9.2 Analyses Supporting Primary Objective(s)

The primary analysis will focus on quantifying the impact of **Complement Theory on changes in Quality of Life Score (QoLS), measured by the FACT-G instrument**, over the trial period. Assessments will occur at baseline, 3, 6, 9, 12, and 18 months.

- **Statistical Model, Hypothesis, and Method of Analysis**

- Primary Estimand (Change in QoLS):
 - Null Hypothesis (H0): There is no difference in the mean change in FACT-G QoLS between participants in the Complement Theory program and those in the control group at specified time points.
 - Alternative Hypothesis (H1): Participants in the Complement Theory program demonstrate a statistically significant improvement in QoLS compared to the control group.
- Baseline Data Analysis: Baseline demographics and characteristics will be provided and summarized in both treatment and control groups. Standardized mean differences (SMDs) will be calculated as the measure of distance between groups. SMDs of 0.2 to <0.5, 0.5 to <0.8 and ≥0.8 are considered small, medium, and large, respectively. Frequencies and percentage will be provided for the binary variables as well as the categorical variables (Yes/No); mean (standard deviation) and median (range) will be computed for continuous variables.
- Method of Analysis: Mixed models for repeated measures (MMRM) will be utilized to analyze changes in FACT-G scores over time, accounting for within-subject correlations. This model allows for the inclusion of both fixed effects and random effects to account for individual variability. In addition, covariate-time interaction terms will be included to guarantee the best results. The strength of the effect from each covariate will be evaluated

through the statistical test significance, i.e., P value, at 95% confidence interval.

- **Handling of Intercurrent Events of Primary Estimand(s)**

- For participants who discontinue the intervention or are non-adherent, we will employ a treatment policy strategy. This means all data collected will be analyzed as per the initial treatment assignment, regardless of the discontinuation or level of adherence, preserving the intention-to-treat principle.

- **Handling of Missing Data**

- Given the potential for missing QoLS data due to dropout or non-response, a multiple imputation (MI) approach will be adopted. The imputation model will incorporate variables predictive of missingness and outcomes to generate plausible values for missing data.

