9.3 Analysis Supporting Secondary Objective(s)

- **Secondary Objective 1: Effect on Employee Absenteeism**

- Statistical Model and Hypothesis:
 - Model: Generalized linear models with a Poisson distribution to compare the number of leave days between groups.
 - Hypothesis: H0: No difference in the number of leave days between groups. H1: A significant reduction in leave days in the intervention group.
- Handling of Intercurrent Events:
 - Analysis will consider any change in employment status as an intercurrent event, with a modified intention-to-treat analysis excluding participants who lose their job unrelated to health status.
- Handling of Missing Data:
 - Worst-case scenario imputation for missing absenteeism data, assuming maximum observed absence for missing periods.
- Sensitivity Analysis:

- Repeating analyses with and without worst-case imputation to evaluate the impact of different missing data assumptions on the outcome.
- **Secondary Objective 2: Impact on Employee Presenteeism**
 - Statistical Model and Hypothesis:
 - Model: Mixed-effects models to analyze changes in work motivation and performance review scores over time.
 - Hypothesis: H0: No difference in changes in motivation and performance scores between groups. H1: Significant improvement in these measures in the intervention group.
 - Handling of Intercurrent Events:
 - Job changes or significant alterations in work responsibilities will be documented and explored in sensitivity analyses to understand their impact on presenteeism outcomes.
 - Handling of Missing Data:
 - LOCF for interim missing data points in motivation and performance scores, acknowledging potential limitations in this approach.
 - Sensitivity Analysis:
 - Analysis excluding participants with significant job changes during the trial to assess the effect of such changes on presenteeism outcomes.

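### Death is foreseeable but has no place in any estimand: by default FACT-G is imputed after death, post-death leave is set to the maximum, and cost handling is undefined

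*Protocol*

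**What the plan says.** **Who is followed, and for how long.** Protocol Section 5.3 admits "Cancer Stage: Stage 1 to 4", and lung cancer is one of the named types. Section 5.4 excludes "ECOG Score 3, 4 or 5". Section 1.3 plans "Regular Assessments up to 18 months".

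**Where death appears.** As a trial outcome it appears only in the adverse-event grading of Section 8.4, as "Grade 5: Results in death (SAE". No estimand in Section 3 or Section 9 mentions it.

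**FACT-G (primary in the Protocol).** The ITT set of Section 9.1 is defined as "Including all randomized survivors, regardless of their adherence with the entry criteria"; survivors there means trial participants, as it does throughout the document. Section 9.2 names stopping the intervention and non-adherence as intercurrent events, both under a treatment-policy strategy. On missing values it says: "Given the potential for missing QoLS data due to dropout or non-response, a multiple imputation (MI) approach will be adopted". The method is MICE with 10 imputations.

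**Leave days.** Section 9.3 uses a Poisson model with no stated offset. It excludes only people whose job loss had nothing to do with their health, and it fills gaps by "assuming maximum observed absence for missing periods". The analysis is repeated without that imputation.

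**Expenditure.** Section 3 of the Protocol defines the estimand as "The difference in mean total healthcare expenditure between the intervention and control groups over a specified period", with 12 and 18 months as examples. It is exploratory there, and Section 9 gives it no model and no missing-data rule. In the Combined protocol and SAP it is primary: Section 9.2 analyses complete cases first and then allows LOCF or MICE. That document does not mention death in its intercurrent-event rules either.

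**The concern.** A FACT-G score after death does not exist. The mean change at 12 and 18 months is therefore undefined for anyone in the all-randomized set who has died, unless the estimand says what to do. MICE would fill those visits with values modelled on people who are alive, so a death would be scored as ordinary quality of life. The same death would be scored as the worst possible absenteeism. For cost, nothing says how it is scored.

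Randomization in Section 6.6 uses cancer type only, not stage, so deaths can differ between the arms by chance. They could also differ by effect: Section 6.2 cites earlier exercise studies with lower cancer mortality. Either way the objectives would be affected in ways that do not agree with one another, and the analyst would be choosing the handling after seeing the data.

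**Working it through.** **1. The plan's own figure.** Section 9.7 inflates 102 evaluable participants for 30% dropout: 102 / (1 − 0.30) = 145.7, rounded up to 146. This reproduces. For FACT-G (70 vs 85, with the stated variance of 20 read as an SD, one-sided 0.05, 80% power) the normal formula gives 2 × (1.645 + 0.842)² × (20/15)² = 22.0 per arm, 44 in total against 42 stated. With 51 per arm, power on these inputs is about 98%. Sample size is not the problem. The 30% (44 people, 22 per arm) is attributed to the length of follow-up, with no separate allowance for death.

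**2. One death traced through the rules.** Take an employed participant who dies at month 5.
- FACT-G: the visits at 6, 9, 12 and 18 months are absent. The person is in the ITT set, no rule separates death from non-response, and MICE fills all four visits.
- FACT-G sensitivity analysis: the only one is per-protocol, and that set leaves out anyone who did not complete the trial. It removes the death and does not show its effect.
- Leave: the remaining periods are missing, the health-unrelated job-loss exclusion does not apply, and each period receives the maximum. The run without worst-case imputation shows this only in part, because it changes the handling of every other gap too.
- Cost: no further cost accrues to a fixed-period total. Under the Combined document's rules the person could instead be dropped as incomplete, or imputed.

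**3. How many.** The documents give no mortality rate, so 18-month mortality m is assumed. Number affected at month 18 = 146 × m; at month 12, with deaths spread evenly, 12/18 of that.
- m = 5%: 7.3 at month 18; 4.9 at month 12 (3% of the set)
- m = 10%: 14.6; 9.7 (7%)
- m = 20%: 29.2; 19.5 (13%)

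**4. Chance imbalance.** At m = 10% with 73 per arm, the SD of the between-arm difference is √(2 × 0.1 × 0.9 / 73) = 0.050, about 5 percentage points.

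**5. Leave.** Assume all are employed, deaths fall on average at mid-period (9 months lost) and the maximum observed absence is 20 days a month. Days added per randomized participant in an arm = m × 9 × 20, which is 9, 18 and 36 days at 5%, 10% and 20%. A 5-point imbalance moves the between-arm difference by 0.05 × 180 = 9 days.

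**6. Cost.** Take the table's control mean of 10,000 for both arms (no true effect), deaths at mid-period, and monthly spending before death f times that of survivors. Arm mean = 10,000 × [(1 − m) + m × 0.5 × f]. With 10% mortality on test and 5% on control:
- f = 1: 9,500 − 9,750 = −250
- f = 2: 10,000 − 10,000 = 0
- f = 3: 10,500 − 10,250 = +250

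The planned difference is 2,000. The sign depends on f, which the documents do not give.

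**The case against.** No sentence says that values after death are to be imputed. Section 9.2 speaks of dropout and non-response, and Section 9.3 does not call time after death a missing period. That is fair: these are defaults, not stated rules. They are nevertheless what the analysis does if run as described. Under Sections 7.3 and 8.4 deaths are known only through reports, and contact ends after failed attempts, so an unreported death is indistinguishable from non-response.

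The plan also contains partial protection. Excluding poor performance status and the medically unfit lowers expected mortality. Section 9.4 compares SAE rates by arm, which would reveal a reported imbalance. The leave analysis is repeated without worst-case imputation. All of this stands, but none of it defines the primary endpoint for a person who has died.

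Three stronger readings are tempting and not supported:
- A reader might infer that death counts as a cost saving and that expenditure would favour the arm with more deaths. The Protocol has no cost analysis rule, the Combined document's rules could drop or impute a person who died, and heavy spending before death can reverse the sign (step 6).
- A reader might assume that date of death is already in hand. SAEs are reported by participants or coaches, the control arm has no coach, records are shared by the participants themselves, and the schedule has no vital-status item.
- A reader might conclude that imputation should be limited to people known to be alive. That would remove participants lost to follow-up, whose status Section 11.1 describes as unknown and whom the imputation is meant to cover.

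**Conclusion.** The point holds for FACT-G and leave days as a consequence of the stated rules applied by default, and for expenditure as an undefined rule with no fixed direction of bias. It goes beyond missing detail: for the Protocol's primary endpoint the imputation would produce values with no meaning, and the planned sensitivity analysis would not expose them.

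The size rests on assumption. At 5% to 20% mortality by month 18, about 7 to 29 of 146 participants would have FACT-G imputed after death at the last visit. The bias in FACT-G points cannot be computed from the documents. The 9-day leave shift holds only under the assumptions in step 5, and the cost figures show only that the sign is open.

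**What to change.** - **Section 9.2:** name death as an intercurrent event. Do not impute FACT-G at visits after a known death. Keep multiple imputation for all other missing values, including those of participants lost to follow-up with unknown status. Add one sensitivity analysis that ranks known deaths below every observed FACT-G score. A mixed model also extrapolates over absent visits, so state that the contrast at each visit refers to participants not known to have died by then, and how it is estimated.
- **Section 9.3:** end the leave-day observation period at death, apply no worst-case imputation after it, and use log time at risk as the Poisson offset.
- **Expenditure:** report deaths and time alive by arm next to the total cost, in both documents.
- **Ascertainment:** identify deaths in the same way in both arms, from Grade 5 SAE reports and the EHR and claims data already collected, and state that some deaths may go undetected.

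The cost is SAP wording, one sensitivity analysis and a uniform check of data already requested. The small downside is that FACT-G at later visits becomes conditional on being alive; the sensitivity analysis addresses this. The change should be made before any results by arm are seen.

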- Multivariate imputation by chained equation (MICE) will be used, i.e., filling the missing data multiple times based on the effect from other covariates by constructing a multivariate regression model. MI is superior to single imputation, as it accounts for the uncertainty of missing values in a more robust way. The number of imputations will be 10, i.e., 10 datasets with imputed data will be created. Each imputed dataset gives a point estimate of the regression coefficients as well as its standard deviation, which will be combined across the 10 datasets to obtain the final estimate and their 95% CIs.
- MICE is flexible and can accommodate variables of different types, as well as complexities such as bounded scales or survey skip patterns, making it well-suited for patient-reported outcomes like QoLS.

- **Sensitivity Analysis**

- To complement our intention-to-treat (ITT) analysis, a per-protocol analysis will be performed, including only participants who fully adhered to the intervention, to explore the effect of adherence on QoLS improvement.

- **Supplementary Analysis**

- Efficacy Analysis: survivors in the treatment and control group will be compared for the outcome variables. The comparison will be evaluated based on both SMD and P value. SMD greater than 0.2 will be considered as acceptable differences (section 3.3 indicated the definition of SMD). Descriptive statistics will be compared between treatment groups and control groups, and P values will be calculated using ANOVA tests comparing means of continuous variables, Brown-Mood test to compare the medians, and Chi-Square tests for binary and categorical variables. The differences will be considered as statistically significant within 95% confidence interval, i.e., P value less than 0.05.

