9.7 Sample Size Determination

- The metric-wise sample size calculation is provided in the table below on alpha as 0.05 and power of 80% for the one-tail test at enrollment ratio = 1.
- While we are conducting the power analysis and sample size calculation based on several variables (outcomes) of interest, the sample size was computed separately for each parameter in the study and the greatest is used to obtain sample size.
- The analysis (detailed below in table) showed that sample of size of 102 is powerful enough for the analysis to cover 100% of primary and secondary metrics.
- Now since we believe that the long follow-up duration of 6 months for our trial will lead to around 30% drop-offs, we decided a final sample size of 146 (73 control, 73 test).

- So even if get 30% or 44 participants drop off we end up with final sample set of 102 (51 control, 51 test) and would be able to come to statistically significant effects ($p < 0.05$) with respect to 100% of primary and secondary metrics.

Metric Segment	Sub Metric	Control Data	Test Data	Assumed Variance	Sample Size
Primary Outcome / Concerns					
Quality of Life Improvement	QoLS Score (FACT-G)	70	85	Variance of 20	42 (21 Control, 21 Test)
Secondary Outcome / Concerns					
Presenteeism	Attitude towards work	2	4	Variance of 1.5	16 (8 Control, 8 Test)
	Employee Performance	0.6	0.7	Variance of 20%	102 (51 Control, 51 Test)
Absenteeism	Working Hours	30	40	Variance of 10	28 (14 Control, 14 Test)
	Vacation Days	0.5	0.3	Variance of 0.15	16 (8 Control, 8 Test)
Exploratory Outcomes					
Cancer Care	Cancer Progression Status	0.85	0.88	Variance of 0.04	46 (23 Control, 23 Test)

	Cancer recurrence status	0.3	0.21	Variance of 10%	32 (16 Control, 16 Test)
Medical Expenditure	Total Healthcare Expenditure (Planned + Unplanned)	10000	8000	Variance of 4000	102 (51 Control, 51 Test)
	No of Urgent Care Visits	3	2.5	Variance of 0.5	28 (14 Control, 14 Test)
	No of ED Visits	5	3.45	Variance of 0.8	10 (5 Control, 5 Test)
	No of unplanned outpatient/office visits (other than ED)	4.28	3.5	Variance of 0.8	28 (14 Control, 14 Test)
	Unplanned Hospitalisations	5	4	Variance of 0.8	18 (9 Control, 9 Test)
	Length of hospital stay	3	2	Variance of 0.8	18 (9 Control, 9 Test)
	No of planned outpatient visits	2	1.8	Variance of 0.3	58 (29 Control, 29 Test)
	No of planned hospital visits	1.25	1	Variance of 0.1	10 (5 Control, 5 Test)
	Length of hospital stay	3	2	Variance of 0.8	18 (9 Control, 9 Test)

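### Ten imputations for the primary FACT-G analysis, with about 30% drop-off expected, leave enough simulation noise for the random seed to decide significance when the result is borderline

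*Protocol*

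**What the plan says.** Section 9.2 of the Protocol makes multiple imputation the method for missing data in the primary endpoint: "Given the potential for missing QoLS data due to dropout or non-response, a multiple imputation (MI) approach will be adopted". The technique is chained equations, and the number is fixed: "The number of imputations will be 10, i.e., 10 datasets with imputed data will be created". Each dataset yields coefficients and their standard deviations, "which will be combined across the 10 datasets to obtain the final estimate and their 95% CIs".

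Section 9.7 expects that the long follow-up "will lead to around 30% drop-offs", which is why 102 participants are raised to 146.

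No random seed, no Monte Carlo error criterion and no rule for raising the number of imputations appears in either document. The Combined protocol and SAP also names 10 imputations in its section 9.2, but there the primary endpoint was healthcare expenditure and complete cases came first. The point therefore concerns the Protocol, where FACT-G is primary and imputation is the stated approach.

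**The concern.** Multiple imputation uses random draws, so two analysts who follow the same plan on the same data get slightly different pooled estimates and P values unless they share a seed. The size of that difference depends on how much information is missing and on the number of imputations. Ten is usually justified by efficiency, meaning how much wider the confidence interval is than with unlimited imputations. That criterion is lenient. The stability of a P value near a threshold needs more imputations.

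What is at stake is the claim of significance for the primary endpoint. If the result lands near the boundary, a different seed could move it across, and the plan says nothing about which seed is used or how large the noise may be.

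**Working it through.** **Inputs**
- Number of imputations m = 10 (section 9.2).
- Drop-off about 30% (section 9.7): "will lead to around 30% drop-offs, we decided a final sample size of 146 (73 control, 73 test".
- FACT-G planning row in section 9.7: "QoLS Score (FACT-G) 70 85 Variance of 20". The spread reproduces the tabulated sizes approximately only if read as a standard deviation, and it is used that way here.
- Threshold: "P value less than 0.05", stated under the supplementary analysis without sidedness. Two-sided is assumed; the one-sided case is checked below.
- FMI: not in the documents. Assumed 0.1 to 0.3.

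**1. The plan's own figure.** 102/(1 − 0.30) = 145.7, rounded up to 146. 30% of 146 is 43.8, or 44, which leaves 102. The stated numbers reproduce.

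**2. Efficiency.** Relative efficiency = 1/(1 + FMI/m). At m = 10 this is 1/1.01 = 0.990 for FMI 0.1 and 1/1.03 = 0.971 for FMI 0.3. The loss is small.

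**3. Monte Carlo error.** The standard deviation of the pooled estimate over seeds, as a fraction of its standard error, is sqrt(FMI/m). Suppose z would be 1.96 (P = 0.05) with unlimited imputations. The approximate 95% range over seeds is then z = 1.96 ± 1.96 × sqrt(FMI/m).

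| FMI | m | sqrt(FMI/m) | 95% range of P over seeds |
|---|---|---|---|
| 0.1 | 10 | 0.100 | 0.031 to 0.078 |
| 0.2 | 10 | 0.141 | 0.025 to 0.092 |
| 0.3 | 10 | 0.173 | 0.021 to 0.105 |
| 0.1 | 100 | 0.032 | 0.043 to 0.058 |
| 0.2 | 100 | 0.045 | 0.041 to 0.061 |
| 0.3 | 100 | 0.055 | 0.039 to 0.064 |

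For a one-sided P of 0.05 at FMI 0.3 and m = 10, z = 1.645 ± 0.339 gives 0.024 to 0.096. Sidedness hardly matters.

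**4. Is the assumed FMI plausible?** A simulation used 73 per arm with 22 per arm missing at month 18, SD 20, and correlation between visits of 0.5 or 0.7. Dropout was early, spread or late, and an analysis of covariance at month 18 stood in for the mixed-model contrast. FMI came out at 0.23 to 0.32. When the P value with many imputations was about 0.03, 16% to 25% of 1,000 ten-imputation runs reported P above 0.05. None of the 100 hundred-imputation runs did.

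**5. The planned effect.** With 51 per arm, the standard error is 20 × sqrt(2/51) = 3.96, so an observed difference of 15 gives z = 15/3.96 = 3.79. That is (3.79 − 1.96)/0.173, or about 10.5 Monte Carlo standard deviations from the threshold at FMI 0.3. No simulated run at this effect exceeded 0.05.

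**6. Where the seed matters.** The vulnerable zone is roughly P = 0.02 to 0.12, that is z = 2.33 down to 1.56. Multiplied by 3.96, this is an observed difference of about 9 down to 6 points. Divided by 20, it is a standardized difference of about 0.46 down to 0.31.

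**7. How often two runs disagree.** Let z vary over trial outcomes as a normal variable with SD 1, and compare two independent ten-imputation runs at two-sided 0.05. To first order, the probability of opposite verdicts is the density of z at the threshold × (2/sqrt(π)) × sqrt(FMI/m). Numerical integration gives:

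| Expected z | FMI 0.1 | FMI 0.2 | FMI 0.3 |
|---|---|---|---|
| 3.79 (planned effect) | 0.9% | 1.2% | 1.5% |
| 0 (null) | 1.3% | 1.9% | 2.4% |
| 1.96 (worst case) | 4.5% | 6.3% | 7.7% |

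**The case against.** The strongest reply is that this seldom matters. On the plan's own assumptions the trial is comfortably powered for FACT-G, and two runs would disagree in only about 1% to 2% of trials at the planned effect or under the null. Nothing is biased, and efficiency is nearly full. This stands. A reader might infer that the primary conclusion is not reproducible in general; the documents do not support that, because only results near the threshold are exposed.

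FMI may also be lower than the drop-off suggests. Section 9.7 ties the drop-off to the length of follow-up, so earlier visits may lose fewer participants. Section 6.1 schedules FACT-G more often than section 9.2 lists, and frequent earlier scores would help the imputation model. Section 11.1 sets limits of 15% for uncollected endpoint data and 10% for loss to follow-up, although these trigger review and are not forecasts. This stands as a reason to start the range at 0.1, where the noise is smaller but not negligible.

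The threshold is not cleanly two-sided 0.05. Section 9.7 sizes the trial "on alpha as 0.05 and power of 80% for the one-tail test at enrollment ratio = 1", and section 9.6 adds O'Brien-Fleming looks. The one-sided check shows that the noise is similar in size, so the point survives.

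Two further readings go too far. The ranges are approximate 95% ranges, not limits, so P cannot be said to fall anywhere within a fixed interval. And 100 imputations would not remove seed dependence: a P value of exactly 0.05 straddles the threshold at any number.

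That borderline results are rare does not make them implausible. Section 9.2 labels standardized differences of 0.2 to below 0.5 as small and counts those above 0.2 as acceptable. The vulnerable zone of 0.31 to 0.46 lies inside that band.

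**Conclusion.** The concern holds as a minor, conditional weakness. With 10 imputations the Monte Carlo error is about 10% to 17% of the standard error for FMI between 0.1 and 0.3, so a borderline primary result can be significant with one seed and not with another. The chance that two runs disagree is about 1% to 2% at the planned effect or under the null, and about 4% to 8% if the expected z sits on the threshold. The size rests on the assumed FMI, on a two-sided 0.05 threshold and on the normal approximation. Bias and loss of power are not at issue.

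**What to change.** In section 9.2 of the Protocol:
- Replace 10 with a larger number of imputations, for example at least 100. This cuts the noise by sqrt(10), from 0.173 to 0.055 of the standard error at FMI 0.3.
- Pre-specify and record the seed. A seed alone makes one run repeatable, but leaves the verdict resting on an arbitrary choice, so both changes are needed.
- Report the Monte Carlo error of the pooled estimate and of the P value, and raise the number of imputations if that error is not small. State beforehand what counts as small. The number 100 is an example, not a derived minimum: 50 imputations would give 0.035 to 0.071 at FMI 0.3.

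The cost is computing time only. No estimand, sample size or trial procedure changes.
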